
Objectives and Hypothesis

1 To perform an outpatient treatment with a Dietary supplement based on sea urchin roe rich in Echinochrome A in patients with sequalae from COVID-19.

a - H1-1: The Dietary supplement improves the clinical status of patients with COVID-19 sequelae

Justification: Treatment with the Dietary supplement rich in Echinochrome A is expected to activate the metabolism of glutathione, improves the functioning of the mitochondria, decreasing the cellular oxidation state and general inflammation of the endothelium, generating an improvement in the clinical status of patients and reducing your recovery time.

b - H1-2: The Dietary supplement based on sea urchin roe rich in Echinochrome A reduces the recovery time of patients with sequelae from COVID-19

Justification: Treatment with the Dietary supplement by activating the metabolism of glutathione and decrease cell oxidation and inflammation of the endothelium, reduces recovery time of the patient.

2 Perform a multidisciplinary follow-up of the evolution of the patient with COVID sequalae, involving clinicians, pulmonologists, neurologists, counselors, biochemists and Researchers.

a - H2-1: The multidisciplinary approach allows a deep understanding of the symptoms of the sequalae from COVID and its evolution

Justification: This approach will allow for a comprehensive analysis. Can be tracked simultaneous clinical, neurological, neurological, cardiological, psychological, biochemical approach, with a adequate analysis of the data, allowing a deeper understanding of the symptoms.

b - H2-2: The multidisciplinary approach generates high adherence to the study and allows a emotional accompaniment of patients, improving their mood Justification: the multidisciplinary approach will allow comprehensive monitoring of patients and increase knowledge about the persistent symptoms found in the patients with sequalae from COVID-19. In addition, psychological support will increase the patient's adherence to treatment and will improve your emotional state when accompanied.

3 Follow up with patients on a daily basis using a partially decentralized through the use of telemedicine in patients with the COVID sequalae.

a - H3-1: The partially decentralized approach by telemedicine allows a daily follow-up of the symptoms of patients with sequalae from COVID, thus relieving the health system

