It is proposed to make a partially decentralized design around the patient following the ACRO recommendations. These studies use digital technologies to optimize resources of the health system and to allow the patient to have daily contact with the objective to accelerate the production of results and create an efficient dynamic of the research process. This type of design puts the patient at the heart of interactions and allows for more efficient bonding of all the actors involved. In this case, the patient with symptoms of persistent Covid-19 is detected in the Hospitals, the treatment is offered to the patient according to medical criteria, the patient's file is filled out with the clinical history and through informed consent, the participant is recruited in this comprehensive care model with intervention. We proceed to complete the Digital Entry Form of the patient where their data is uploaded and a photo of the informed consent document is attached signed, the group of CONICET-UNPSJB Researchers receives the information about the patient and by randomized algorithm, the delivery of the nutraceutical or the placebo is determined and sent to the patient's address along with pertinent information. The ID of each patient in the entire Health System telemedicine will be your ID. Once loaded, the link of the digital self-tests will be sent to your WhatsApp designed for this study, which the patient must complete and send daily as a health report and you can use it whenever she needs it. SKYMED is governed by Law 25,326 on Data Protection Personal and Law 26,529 of the Right of the Patient and has the due Confidentiality Agreements that protect and commit all parties in your application during the use of the platform. Starting from that moment the Muñiz Hospital Hemostasis Team and the Team of Psychological Consultants Receive patient information. From here, through the calendar of the telemedicine system SKYMED organizes shifts for each patient with Hospital Muñiz for blood collection, interviews with the psychological accompaniment and the medical follow-ups by the different doctors and hospitals involved. The patient fills out the form every day and this information can be monitored instantly. If the patient has symptoms that show deterioration, sends an alert to the medical team through the triage system that SKYMED has based on artificial intelligence. The patient has an instant messaging interface to make inquiries during the treatment in addition to the weekly interviews with the team of psychological consultants and the Monthly visits to hospitals. The evolution of the patient is carried out weekly and at the end of the study the results are already very advanced to be able to conclude on them. This approach seeks to accompany the patient throughout the medical study from a multidisciplinary, considering the practical aspect of decentralization with the emotional care that patients with persistent COVID syndrome require.

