The psychological accompaniment will be carried out through a weekly virtual Zoom meeting of 30 minutes during the three months of treatment with the psychological consultant, in which he will be given accompaniment and emotional support hoping to sustain their adherence to it (Centered Approach in the Person. Likewise, face-to-face evaluations will be carried out with specialist doctors, at the beginning of the medical test and once a month after beginning the treatment, until its completion. In these evaluations will carry out a complete clinical and psychological study. Face-to-face evaluations are also carried out with the specialists, at the beginning of the medical test and once a month after starting the treatment, until its completion. In these evaluations, a complete clinical study will be carried out, evaluating the presence of cough, chest pain, dyspnea by mMRC scale, quality of life by EuroQOL scale, spirometry will be performed (FVC, FEV1, FEV1/FVC), the walk test of 6 minutes, a HRCT of the Chest, an electrocardiogram, the evaluation of fatigue measured with the MFI scale, the cognitive evaluation will be carried out with the MMSE (minimental State) scale, ACE-R (Addenbrooke's Cognitive Examination), attention by San of Digits forward, Digits and signs (WAIS-III), Trial Making A and Stroop Test; executive function with Trial Making B, word generation (phonological verbal fluency), FAB (Frontal Assessment Battery), clock test (on command) and analogies (WAIS-III); Language will be evaluated with the Boston Nomination Test and through semantic verbal fluency; Verbal Memory will be evaluated by the RAVLT test (Rey auditory verbal learning test), Visual Memory with the Rey Figure (evocation and recognition), Visuospatial ability with the Rey Figure (copy) and the clock test (Copy) and Mood assessment with the Beck Inventory. Finally, blood samples will be taken from the patients to perform a complete blood count, platelets, white blood cells and formula in absolute and relative values, C-Reactive Protein, Ferritin, D-Dimer and Von Willebrand Factor.

SKYMED telemedicine

The telemedicine System and Remote Patient Control SKYMED complies with the quality standards established in the Design Quality Manual for ACRO Decentralized Clinical Trials (Association of Clinical Research Organizations for its acronym in English), regarding the possibility of entering data by the patient and the equipment intervening remotely, as well as

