This research project will not affect human rights nor will it be the cause of any eventual damage to the environment, animals and/or future generations. All work done previously carried out in compliance with the Biosafety and Environmental Safety Standards in force, so its realization will not have any impact on the environment. Biological material (blood samples human) will be processed in a biological safety cabinet and all the elements and reagents used properly discarded following the standards indicated by the Health and Safety Committee of the Hospital F. J. Muñiz. In this sense, the Hospital has a pathological waste management service. On the other hand, the methodology included in this project has been endorsed by the Ethics Committees of the hospitals.

Physicians will invite patients and/or their immediate family members to participate in the research study, explaining in a detailed and understandable way the characteristics of the study and future studies related to sequelae in COVID-19. Informed consents are approved by the Committees of Ethics and/or Teaching and Research of the Hospitals involved. In Argentina there is a law that protects personal information (Law No. 25,326 on Data Protection Personal) that establishes the integral safeguard of data settled in files or records, be they public or private, to guarantee the right to honor and privacy of people. When is made reference to "Client's personal data" is about the personal data of which the Institutions authorized are controllers and that OcusCloud processes in the course of providing the SaaS (Software as a service) SkyMeD. The terms "controller", "processor", "process", "processed", processing" and "personaldata" used, are defined according to the Union Directive 95/46/EC European Union, except as defined by the corresponding data protection legislation. OcusCloud guarantees under the

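### As written, chest HRCT is done at every face-to-face evaluation: four CT scans per patient in three months, with no stated use for the two in the middle

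*Protocol*

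**What the plan says.** The relevant text is the paragraph on face-to-face evaluations in the Protocol section on the partially decentralized design, just before the heading on SKYMED telemedicine.

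- **Visit schedule:** evaluations by the specialists take place "at the beginning of the medical test and once a month after starting the treatment, until its completion".
- **Content of the visits:** the next sentence begins "In these evaluations, a complete clinical study will be carried out" and continues as one undivided list: symptoms, dyspnea and quality-of-life scales, spirometry, the 6-minute walk, "a HRCT of the Chest, an electrocardiogram", fatigue and a long cognitive battery.
- **Length of treatment:** given in the same section, in the sentence on psychological support: "during the three months of treatment".

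HRCT is named nowhere else in the text. No sentence ties it to particular visits, to an abnormal earlier scan or to a physician's judgement.

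Under Objectives and Hypothesis, H1-2 states that the supplement "reduces the recovery time of patients with sequelae from COVID-19", and H2-1 concerns understanding the symptoms and how they evolve. The H2-1 justification describes the follow-up as "Can be tracked simultaneous clinical, neurological, neurological, cardiological, psychological, biochemical approach". Neither hypothesis is defined by a CT measure.

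**The concern.** A site that follows this paragraph scans every patient, on supplement or placebo, at each monthly visit. Every other listed test can be repeated without radiation; HRCT cannot. Repeating it monthly therefore needs a purpose of its own, and the protocol gives none.

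The stake is patient safety. The number of scans is fixed by the visit procedures in the protocol, and a later analysis plan cannot undo a scan already taken. The point does not concern power, type I error, drop-out or the decentralised design.

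**Working it through.** **Number of scans.** The protocol states no number, so it has to be derived.

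- Evaluations = 1 at the start + 1 per month × 3 months = 4.
- HRCT per evaluation = 1, because the list is not split by visit.
- Scans per patient = 4 × 1 = 4.

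If no monthly visit fell at the end of treatment, the count would be 3. The schedule runs until treatment is completed, which supports 4. With scans at the first and last evaluations only, the count is 2.

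**Exposure.** The ratio 2/4 = 0.5 holds at any dose per scan. The protocol gives no dose; 1 to 7 mSv per scan is an assumption:

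| Schedule | Scans | At 1 mSv | At 7 mSv |
|---|---|---|---|
| As written | 4 | 4 mSv | 28 mSv |
| First and last evaluation | 2 | 2 mSv | 14 mSv |

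**Is there a stated use for monthly scans?** The hypotheses on recovery time and symptom evolution are longitudinal, so repeated data are needed. The protocol already collects them. On the daily self-report it says "The patient fills out the form every day and this information can be monitored instantly". Spirometry, the 6-minute walk, and the dyspnea and fatigue scales are repeated monthly. These do not show lung structure, but no stated outcome requires lung structure every month.

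**What would be lost without the intermediate scans.** Suppose a CT contrast between arms at month 3 were wanted. Let *d* be the share of patients who miss the last scan but have the month-2 scan, and *r* the partial correlation between month-2 and month-3 values given baseline. Assume that the last scan is missing at random. Relative to the variance of the contrast among those with a final scan, using the month-2 scans gives

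(1 − r²) + r²(1 − d) = 1 − d·r².

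The variance without the intermediate scans is larger by 1/(1 − d·r²) − 1:

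| d (assumed) | r (assumed) | 1 − d·r² | Extra variance |
|---|---|---|---|
| 0.10 | 0.5 | 0.975 | 2.6% |
| 0.10 | 0.8 | 0.936 | 6.8% |
| 0.20 | 0.5 | 0.950 | 5.3% |
| 0.20 | 0.8 | 0.872 | 14.7% |

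With complete data, d = 0, the ratio is 1 and nothing is lost. The formula covers variance only; if missing the final scan depended on the interim CT values, some protection against bias would be lost as well.

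**The case against.** **The text may not mean monthly CT.** It is a rough narrative translation, the count of four is inferred, and the long list could be a catalogue of measures rather than a per-visit schedule. This is a fair caution, and it is why the point is put as a literal reading. The list is nevertheless introduced as what is done at the evaluations. The singular wording does not separate HRCT from the ECG, which is written the same way. If fewer scans are intended, the same line still has to be added.

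**Pulmonary follow-up is a stated aim.** Objective 2 names pulmonologists, and chest CT belongs to their work; the H2-1 justification names no pulmonary discipline at all, so its silence on imaging proves little. This weakens that one piece of evidence. It explains why HRCT is in the study, but not why it is repeated monthly. The weekly analyses do not explain it either.

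**No formal outcome is named for any test, and details may sit in an analysis plan that is not available here.** Both statements are true, and the missing CT outcome is part of a wider gap. But visit procedures are set in the protocol, and only this test carries radiation.

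**A justification may exist elsewhere.** The protocol states that "the methodology included in this project has been endorsed by the Ethics Committees of the hospitals", and the consent pages were not available for this review. Approval is not a rationale, though a reason may exist in papers not seen.

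**The figures rest on assumptions, and two scans is a choice.** This stands in part. The dose, missingness and correlations are assumed, and the protocol does not favour two scans over, for example, baseline only. The halving relative to the literal schedule depends on none of those assumptions.

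**Conclusion.** The concern holds. Followed literally, the protocol requires four chest HRCTs per patient in three months, with no limit by visit, no clinical condition and no outcome that uses a monthly course. Limiting HRCT to the first and last evaluations removes two of the four scans. That conclusion rests on the three-month treatment, on a visit at its completion and on reading the list as applying to every evaluation. The mSv and variance figures are illustrations under stated assumptions.

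This does not show that two scans are required, since the protocol states no CT comparison at all. It shows that the monthly frequency has no stated use. The change should be made. Confidence is medium, because the sponsor may already intend fewer scans or hold a reason that the text does not give.

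**What to change.** Take HRCT out of the list of tests done at every evaluation and add one line:

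> *HRCT of the chest at the baseline and end-of-treatment evaluations only; any other scan only on clinical indication by the treating physician.*

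All other monthly tests stay as they are. A before-and-after CT comparison remains possible, and a patient who deteriorates can still be scanned. If the sponsor wants monthly scans, the protocol should instead name the CT outcome that uses them.

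The change costs one line of text and saves scanner time and money. The downside is that there would be no routine CT data at months 1 and 2, and so less information on patients who leave before the final scan.
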